Primary Objectives	
 1. To determine the prevalence of TGNB persons undergoing chest masculinization surgery who have an elevated lifetime risk of breast cancer development and prevalence of those who undergo genetic counseling. 2. To determine whether those TGNB persons at elevated risk of breast cancer development choose to undergo risk-reducing mastectomies as part of their chest masculinization surgery. 3. To assess and compare the self-perceived breast cancer risk with calculated risk.
Primary Endpoints	
 1. The percentage of all participants undergoing chest masculinization surgery who are at elevated lifetime risk of BC development (i.e., >17%) and those who undergo genetic counseling. Lifetime BC risk will be estimated utilizing the Gail and IBIS models. 2. The percentage of those participants with moderate to high lifetime BC risk or pathogenic germline variant that say they would choose to undergo a risk-reducing mastectomy. 3. The accuracy of self-perceived BC risk, as measured by the Visual Analog Scale (VAS), and the personalized BC risk assessment taken after the VAS.
Main Eligibility Criteria	
 • ≥18 years old. • Assigned female or intersex at birth and identify as non-cisgender. • Considering undergoing gender-affirming chest masculinization surgery. • Ability to communicate in English. • Ability to understand a written informed consent document, and the willingness to sign it.
Study Design	Prospective, single-arm interventional pilot study designed to test whether a breast cancer risk assessment, genetic testing (when applicable), and surgical oncologist consultation can inform those TGNB patients at elevated risk for breast cancer development to undergo risk-reducing mastectomies in tandem with their gender-affirming chest masculinization surgery.

Intervention	Breast cancer risk assessment and education.
Number of Subjects	35 patients (100 patients screened)
Subject Participation Duration	Breast cancer risk assessment will take approximately 30 minutes. Additionally, we wish to follow participants via record review for up to 1 year.
Estimated Time to Complete Enrollment	One year

STUDY SCHEMA

STUDY CALENDAR

Assessments and Procedures	Screening/ Enrollment	Visit 1	Cancer Genetics Clinic Visit ^b	Visit 2 ^c	Follow-up ^d
	Day -60 to -1	Day +1			
Eligibility Confirmation	X				
Informed Consent	X	X ^a			
Patient Registration	X	X ^a			
Visual Analog Scale		X			
Personalized BC Risk Assessment (Gail and/or IBIS model)		X			
Genetic Counseling ^b			X ^b		
Genetic Testing ^b			X ^b		
Surgical Oncologist Risk-Reducing Mastectomy Counseling Session ^c				X ^c	
Data Collection		X	X	X	X
Adverse Events Collection		X	X	X	

Footnotes

- ^a During Visit 1, the study team will be available to answer any additional questions the potential participant may have about the study and confirm whether they were consented. If not done so already and as an option, a potential participant will have the opportunity to sign the informed consent form in person.
- ^b Only those study participants with a family history suggestive of a pathogenic variant and/or with an elevated breast cancer risk who meet genetic testing guidelines ([Appendix 2](#))^{1, 2} will be referred to the Cancer Genetics Clinic to undergo a formal genetic counseling session and possible germline genetic testing. Genetic testing will be performed via the Ambry Genetics® Panel per institutional standards. See [Section 6.3](#) for additional details.
- ^c Only those study participants with an estimated lifetime breast cancer risk >17% (defined by the Gail model [<https://ibis.ikonopedia.com>]) and/or IBIS model [<https://www.mdcalc.com/calc/3647/gail-model-breast-cancer-risk>]) or with a pathogenic germline mutation known to increase breast cancer risk will be offered to meet with the PI to discuss the utility of considering risk-reducing mastectomies as part of their chest masculinization surgery. If a subject is referred to the Cancer Genetics Clinic, Visit 2 is to occur after their Cancer Genetics Clinic visit.
- ^d Participants with an estimated lifetime breast cancer risk >17% may be followed-up once within 60 days after the end of the funding period to determine if they either (i) underwent their chest masculinization surgery with or without the risk-reducing mastectomies, (ii) scheduled but did not undergo their chest masculinization surgery with or without the risk-reducing mastectomies, or (iii) say they would choose to schedule/undergo risk-reducing mastectomies as part of their chest masculinization surgery. Regarding (i) and (ii), follow-up data will only be collected from participants that had their procedure(s) performed by a MCW Plastic Surgery team member (study Co-Is) and, in certain instances, the study PI.

LIST OF ABBREVIATIONS

AE	adverse event
BC	breast cancer
CDH1	cadherin 1
CFR	Code of Federal Regulations
CHEK2	checkpoint kinase 2
Co-I	Co-investigator
CTCAE	Common Terminology Criteria for Adverse Events
CTEP	Cancer Therapy Evaluation Program
CTO	Clinical Trials Office
CTSI	Clinical and Translational Science Institute
DSMC	Data and Safety Monitoring Committee
DSMP	Data and Safety Monitoring Plan
FH	Froedtert Health System
GCP	Good Clinical Practice
HIPAA	Health Insurance Portability and Accountability Act
IBIS	Tyrer-Cuzick Breast Cancer Risk Evaluation Tool
ICH	International Council for Harmonisation
ICMJE	International Committee of Medical Journal Editors
IRB	Institutional Review Board
MCW	Medical College of Wisconsin
MCWCC	Medical College of Wisconsin Cancer Center
MRI	magnetic resonance imaging
NCI	National Cancer Institute
PALB2	partner and localizer of BRCA2
PHI	protected health information
PI	Principal Investigator
PTEN	phosphatase and tensin homolog
SAE	serious adverse events
SOP	standard operating procedure
SRC	Scientific Review Committee
TGNB	transgender and nonbinary persons
US	United States

1.0 BACKGROUND

1.1 Breast Cancer in Transgender and Nonbinary Persons

The population of transgender and nonbinary persons (TGNB) in Wisconsin and the United States (US) is steadily increasing and as this population grows, the number of individuals seeking gender-affirming therapies, including gender-affirming operations and gender-affirming hormone therapy, is also increasing.³⁻⁵ In calendar year 2021 alone, the Froedtert & Medical College of Wisconsin Inclusion Health Clinic cared for >700 TGNB persons, and this patient population has been steadily increasing since the clinic opened in 2018. An example of gender-affirming surgery is chest masculinization surgery, colloquially called top surgery, in which the majority of breast tissue is removed in a person with a female sex assigned at birth to allow the chest to appear masculine.⁶ While chest masculinization surgery removes most glandular breast tissue, some breast tissue is often left behind to allow for appropriate cosmetic contouring of the chest (**Figure 1**) and is not considered synonymous to an oncologic risk-reducing mastectomy.^{6, 7} An oncologic risk-reducing mastectomy seeks to remove all breast tissue in an effort to minimize the future risk of breast cancer

[figure not shown]

Figure 1. Before (A) and after (B) photos of a TGM after chest masculinization surgery

(BC) development in persons with an elevated lifetime risk of breast cancer.⁸⁻¹⁰ Additionally, there is an increasing number of reported cases of TG men developing BC after chest masculinization surgery, secondary to the lack of data to support routine personalized BC risk assessment prior to chest masculinization surgery or for BC screening after chest masculinization surgery.^{7, 11-14} Although gender-affirming therapies are associated with improved mental health outcomes and well-being for TGNB persons,¹⁵ the potential long-term effects of these therapies on overall health, including future breast cancer risk, are not well understood.¹⁶⁻¹⁸

BC is the most common non-skin cancer in cisgender women. The current average lifetime risk for cisgender women is approximately 13% for a person who lives to be age 85 years in the United States.^{19, 20} A person's lifetime risk of BC development may be dramatically impacted by a family history of BC, increased breast density, a personal history of atypical hyperplasia, lobular carcinoma in situ, high-dose radiation to the chest before age 30, or inherited genetic mutations in BC susceptibility genes.²¹⁻²⁹ Two well-validated models have been developed to estimate an individual's personalized percent lifetime BC risk: the Gail Model³⁰⁻³⁶ and the Tyrer-Cuzick BC Risk Evaluation Tool (also called IBIS) that incorporate personal history (e.g., first age at menarche, history of breast biopsies) and family breast and ovarian cancer history to calculate future breast cancer risk compared to the average cisgender woman.³⁷⁻⁴³ Both models provide a percent estimate of a person's lifetime risk compared to the average women (ex: 35% lifetime risk for a person compared to 12.5% for average risk peer). Cisgender women with a moderate lifetime BC risk (17%-30%)⁴⁴ can be offered BC screening at an younger age (prior to age 40 years), enhanced BC screening with magnetic resonance imaging (MRI), or risk-reducing medications such as tamoxifen or raloxifene.⁴⁵⁻⁴⁹ Those with a high lifetime BC risk, defined as >30%,⁴⁴ can be offered the previous options and may also consider risk-reducing mastectomies, a procedure reserved for this group given its potential risks and complications.^{1, 9, 50-52} High and moderate penetrant pathogenic variants (BRCA1/2, PTEN, CDH1, PALB2, CHEK2, ATM, etc.) are known to elevate BC risk.^{2, 53-57} Pathogenic variants (mutations) may be found through exploratory

processes, such as commercially available kits like 23andMe®, or through formal evaluation by a healthcare provider based on personal or family history. Risk-reducing mastectomies are generally offered to persons with a known pathogenic variant or a lifetime BC risk >30%.^{8, 58, 59} While the ability to reduce BC incidence in these populations with risk-reducing mastectomies is well documented, there is insufficient data to determine if the operation provides a clear mortality benefit, with the exception of persons with a BRCA1 mutation.^{8, 9, 50, 58, 59}

Self-perceived BC risk has the potential to influence risk-modifying behaviors such as alcohol and smoking use, uptake of cancer screening recommendations, and has been demonstrated to influence the decision for risk-reducing mastectomies in cisgender women with an elevated lifetime BC risk.⁶⁰⁻⁶² There is no contemporary data on perceived BC risk prior to chest masculinization surgery in TGNB persons, which may potentially influence an individual's decision to undergo chest masculinization surgery ± risk-reducing mastectomies. Given that an increasing number of TGNB persons are undergoing gender-affirming chest masculinization surgery and that no data exists on the operation's ability to reduce the incidence of BC, a clear opportunity exists to perform routine personalized BC risk assessment (± genetic testing) prior to chest masculinization surgery to identify those persons with a high lifetime BC risk who may benefit from undergoing oncologic risk-reducing mastectomies as part of their gender-affirming chest masculinization surgery.⁶³ Currently, these individuals do not undergo personalized BC risk assessment prior to chest masculinization surgery. Additionally, there is a need to examine both the accuracy of self-perceived BC risk in TGNB persons and how it may influence gender-affirming surgical decision making. Understanding BC risk in TGNB persons is a critical step in mitigating cancer disparities in this underserved population in Wisconsin and across the United States and to ensure patients are informed of this risk prior to undergoing chest masculinization surgery.

The Froedtert & MCW Inclusion Health Clinic opened in July 2018 and is located on the Milwaukee Regional Medical Center grounds within the Sargeant Health Center. The clinic is focused on providing health care for LGBTQ+ individuals. Services include primary and preventive care, obstetrics and gynecology, HIV prevention, gender-affirming care, and psychiatric care. The clinics are the only ones of its kind in Wisconsin and in the 2020-2021 fiscal year, cared for >1,600 individual patients, of which >600 identify as transgender. The unique relation with the Inclusion Health Clinic, the Southeastern Wisconsin LGBTQ+ community, and a skilled Plastic Surgery team allow for a unique opportunity to conduct this investigation.

1.2 Rationale

The goals of this pilot study are to 1) determine the percent of TGNB persons undergoing chest masculinization surgery who have an elevated lifetime risk of BC development (>17%) or a pathogenic genetic mutation that increased the risk of BC development (BRCA1/2, ATM, etc.), 2) measure the percent who are at risk and say they would choose to undergo risk-reducing mastectomies as part of chest masculinization surgery, and 3) assess and compare self-perceived BC risk with calculated risk. The results of this study will substantially inform TGNB patients and surgeons on the utility of personalized BC risk assessment prior to chest masculinization surgery and the accuracy of self-perceived BC risk in TGNB persons. This project has the potential to set a new standard of care that all TGNB persons should undergo a personalized BC risk assessment prior to gender-affirming surgery.

2.0 OBJECTIVES AND ENDPOINTS

This prospective, single-arm interventional pilot study is designed to test whether a breast cancer risk assessment, genetic testing (when applicable), and surgical oncologist consultation can inform those TGNB patients at elevated risk for breast cancer (BC) development to undergo risk-reducing mastectomies in tandem with their gender-affirming chest masculinization surgery. This study is expected to collect and analyze novel data that describes the prevalence of elevated BC risk in the TGNB population and the concordance between self-perceived BC risk and calculated risk, a pressing need for which little is known.

2.1 Primary Objectives

1. To determine the prevalence of TGNB persons undergoing chest masculinization surgery who have an elevated lifetime risk of breast cancer development and prevalence of those who undergo genetic counseling.
2. To determine whether those TGNB persons at elevated risk of breast cancer development choose to undergo risk-reducing mastectomies as part of their chest masculinization surgery.
3. To assess and compare the self-perceived breast cancer risk with calculated risk.

2.2 Primary Endpoints

1. The percentage of all participants undergoing chest masculinization surgery who are at elevated lifetime risk of BC development (*i.e.*, >17%) and those who undergo genetic counseling. Lifetime BC risk will be estimated utilizing the Gail and IBIS models.
2. The percentage of those participants with moderate to high lifetime BC risk or pathogenic germline variant that say they would choose to undergo a risk-reducing mastectomy.
3. The accuracy of self-perceived BC risk, as measured by the Visual Analog Scale (VAS), and the personalized BC risk assessment taken after the VAS.

3.0 SUBJECT POPULATION AND ELIGIBILITY

MCW must follow all MCW IRB requirements and policies regarding subject participation, found here: <https://www.mcw.edu/HRPP/Policies-Procedures.htm>

3.1 Subject Population

Non-cisgender adults seeking chest masculinization surgery (top surgery).

3.2 Eligibility Criteria

The study team will evaluate eligibility according to the following criteria. Subjects must meet all inclusion and none of the exclusion criteria to be registered on to the study. Any questions or concerns regarding eligibility should be directed to the PI, [name] ([contact]).

No waivers of protocol eligibility will be granted.

3.2.1 Inclusion Criteria

A potential study subject who meets all of the following inclusion criteria is eligible to participate in the study.

1. ≥ 18 years old.
2. Assigned female or intersex at birth and identify as non-cisgender.
3. Any individual considering undergoing gender-affirming chest masculinization surgery
4. Ability to communicate in English.
5. Ability to understand a written informed consent document, and the willingness to sign it.

3.2.2 Exclusion Criteria

A potential study subject who meets any of the following exclusion criteria is ineligible to participate in the study.

1. < 18 years old.
2. Assigned male sex at birth.
3. Previously underwent chest masculinization surgery or any form of oncological mastectomy for the purposes of risk-reduction or cancer treatment.
4. Any previous or current history of breast cancer, including ductal carcinoma in situ (DCIS).
5. Inability to communicate in English.

4.0 ACCRUAL GOAL AND STUDY DURATION

The Froedtert and MCW Plastic Surgery Clinics see 75-100 individuals seeking top surgery per year. In 2022, MCW Plastic Surgeons performed 55 chest masculinization operations. Based on our study protocol and budget allotment, we expect to screen 100 patients and recruit 35 participants for this study.

The study is estimated to reach completion approximately 12 months from the time the study opens to accrual.

5.0 PATIENT RECRUITMENT AND REGISTRATION

[figure not shown]
TGNB individuals seen in the Plastic Surgery Clinic for surgical consultation for gender-affirming chest masculinization surgery will be given the opportunity to participate in the study. The PI or [name], APNP will review the Plastic Surgeons' schedules to notify plastic surgeons of potential eligible participants. Patients will be provided a flyer that provides an overview of the study premise, measures, and study team contact information.

Once an individual confirms interest in the study, they will be screened by the PI for eligibility through Epic and then contacted via phone and/or email to discuss the study, answer any question, and the potential participant will be provided with an electronic and encrypted copy of the study's consent form, if interested in participating. Participants may provide their electronic signature and emailed back to the PI prior to Visit 1, at the time of Visit 1, or if meeting in person can provide a written signature.

Eligible participants who want to participate will be scheduled for a 30-minute appointment (Visit 1) in the Breast Care Clinic, located within the Froedtert and Medical College of Wisconsin Clinical Cancer Center, with either [name], APNP or the PI. Eligible participants will also be given the option to have only a telephone or virtual visit (at the individuals' discretion). Patients who wish to meet in person for this screening assessment will be billed for services if seen formally in-person in the Breast Care Clinic. Participants will be incentivized to participate by receiving a \$100 gift card.

6.0 STUDY DESIGN, PROCEDURES, AND MEASUREMENTS

6.1 Overview of the Study Design Workflow

*Activities that occur after the personalized BC risk assessment are participant choice, standard practice, and will be collected as part of study data.

6.2 Visit 1: Breast Cancer Risk Assessment, Risk Categorization, and Initial Counseling

Participants will be scheduled within 60 days of initial screening and consent to undergo a personalized BC risk assessment utilizing the Gail and IBIS tools, which are both validated and widely used assessments.³⁷⁻⁴³ During Visit 1, participants will identify their self-perceived lifetime BC risk on the Visual Analog Scale ([Appendix 1](#)) as part of the initial study intake, which will also acquire identifiable patient data (name, date of birth, and medical record number) and demographic information (race, ethnicity, age, sex assigned at birth, gender, etc; see Section 6.5 for a comprehensive list of data factors to be collected). The PI and [name], APNP will enter the risk estimates from the Gail (<https://ibis.ikonopedia.com>) and IBIS

(<https://www.mdcalc.com/calc/3647/gail-model-breast-cancer-risk>) models into the same intake form, and calculate the mean BC calculated risk as the average of the two models:

$$\text{Mean Lifetime BC Risk} = \frac{\text{Risk from Gail Model} + \text{Risk from IBIS Model}}{2}$$

For participants <35 years old, in which Gail is not validated, only the IBIS lifetime BC risk will be used, and a mean lifetime risk will *not* be calculated.

Participants with an **average** lifetime BC risk, defined as $\leq 17\%$,⁴⁴ will be recommended to continue their gender-affirming operation as planned and will not be scheduled for a second visit.

Those with a **moderate** lifetime BC risk, defined as 17-30%, will be counseled on their elevated risk and the option to consider risk-reducing mastectomies as part of their gender-affirming chest masculinization operation. This option will be provided for moderate-risk persons, given the unclear long-term BC risk reduction from chest masculinization surgery alone. Moderate risk individuals will also be counseled on standard risk-reducing strategies, including lifestyle modifications, risk-reducing endocrine therapy options, and increased breast cancer screening strategies.

Participants with a **high lifetime** BC risk, defined as $>30\%$, will be counseled on the potential benefit of undergoing risk-reducing mastectomies as part of their gender-affirming chest masculinization operation, and also be counseled on standard risk-reducing strategies, including lifestyle modifications, risk-reducing endocrine therapy options, and increased breast cancer screening strategies.

Those participants with an elevated lifetime risk based on family history, or with an unknown family history (per NCCN guidelines) will be offered to meet with a Genetic counselor to consider genetic study (see [Section 6.3](#)).

Those with a moderate or high risk and/or family history suggestive of pathogenic variant who decline further genetic testing or a 2nd visit with [name] will be given the opportunity to express why they declined.

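### Section 6.2's rule for lifetime risk of 17% or less makes no exception for a participant already known to carry a pathogenic variant, against Study Calendar footnote c; footnote d also omits carriers at that score

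*Combined protocol and SAP*

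**What the plan says.** **Section 6.2** sets three categories by model score. Participants in the lowest (17% or less) "will be recommended to continue their gender-affirming operation as planned and will not be scheduled for a second visit". The sentence has no exception.

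**Study Calendar, footnote c** offers the Visit 2 discussion to those above 17% "or with a pathogenic germline mutation known to increase breast cancer risk will be offered to meet with the PI". It sets no limit on the carrier's score or on when the variant was found.

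**Section 6.3** offers the same discussion to people who have genetic testing and prove to carry a breast cancer variant. Referral to genetics requires a suggestive family history and/or an elevated risk that meets the Appendix 2 criteria. Section 6.2 adds an unknown family history.

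**Section 1.1** recognises that variants can come to light outside a formal evaluation, through sources "such as commercially available kits". It also treats a known variant as an indication for risk-reducing mastectomy in its own right, separate from a risk above 30%.

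**Primary endpoint 2 (section 2.2)** has as its denominator participants at moderate or high risk or with a pathogenic germline variant. Its numerator is those who say they would choose risk-reducing mastectomy.

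**Study Calendar, footnote d** reads: "Participants with an estimated lifetime breast cancer risk >17% may be followed-up once within 60 days after the end of the funding period". Its item (iii) is whether they "say they would choose to schedule/undergo risk-reducing mastectomies as part of their chest masculinization surgery".

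**The concern.** A known carrier scoring 17% or less gets opposite instructions depending on which part of the protocol staff open. Under 6.2 the carrier is told to go ahead as planned and is not seen again. Under footnote c the carrier is offered a surgical oncology discussion first. Section 1.1 explains why this matters: chest masculinization often leaves some breast tissue and is not equivalent to a risk-reducing mastectomy. Average-risk advice would therefore reach someone whom the protocol itself regards as a candidate for the larger operation, shortly before surgery that cannot be undone.

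There is a smaller data consequence. Endpoint 2 needs a stated choice from every carrier. The one follow-up contact that names that choice is open only to people above 17%. This leaves out carriers at 17% or less, including those found by testing during the study, whose route to Visit 2 is otherwise clear.

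**Working it through.** **1. The rules side by side, for participants scoring 17% or less**

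| Participant | 6.2 | Footnote c | 6.3 | Footnote d | In endpoint 2? |
|---|---|---|---|---|---|
| No variant | No Visit 2 | No offer | No offer | No | No |
| Tested during the study, variant found | No Visit 2 on the score | Visit 2 offered | Visit 2 offered | No | Yes |
| Variant already known at Visit 1 | No Visit 2 | Visit 2 offered | Not named | No | Yes |

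The third row is the conflict. In the second row 6.3 settles the visit, but the footnote d gap remains.

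**2. Can the known carrier arise?** The eligibility criteria (3.2.1 and 3.2.2) exclude prior breast cancer and prior mastectomy, not carriers. Section 1.1 foresees variants found by commercial kits.

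**3. Does the genetics route catch this person?** Not necessarily. The 6.3 triggers are family history and elevated risk. The first Appendix 2 criterion concerns a variant in a blood relative; none of the printed criteria names the participant's own earlier germline result. A carrier with a suggestive or unknown family history may be referred; one without need not be.

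**4. Do other data items fill the gap?** In part. The Protocol Summary says "we wish to follow participants via record review for up to 1 year", with no score limit. Data are collected at Visit 2, 6.4 lets those who decline give reasons, and 12.1 mentions entering the decision for surgery. Section 6.5 lists genetic testing with results and whether risk-reducing mastectomy took place. None of these requires the stated choice from a carrier who never reaches Visit 2, and no item asks for a variant known before enrolment.

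**5. The plan's own figure.** Section 9.1 assumes 4 of 35 at elevated risk and a 10% margin with an exact 90% interval. Clopper-Pearson: lower limit = Beta quantile(0.05; 4, 32) = 4.0%; upper limit = Beta quantile(0.95; 5, 31) = 24.3%; half-width = (24.3 − 4.0)/2 = 10.1 points. The stated margin reproduces and this point does not depend on it.

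**6. Illustration for endpoint 2.** Assume that the 4 people in 9.1 form the denominator and that one carrier at 17% or less should be added. Neither is given as such in the documents. If k of the 4 choose mastectomy and the carrier's answer is a (0 or 1), the change is (k + a)/5 − k/4 = (4a − k)/20.

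- Largest shift: 4/20 = 20 points (0/4 = 0% to 1/5 = 20%, or 4/4 = 100% to 4/5 = 80%).
- Middle case: 2/4 = 50% (exact 90% CI 9.8% to 90.2%) becomes 2/5 = 40% (7.6% to 81.1%) or 3/5 = 60% (18.9% to 92.4%).

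**7. How likely is a known carrier?** The documents give no rate. If a share q of participants are known carriers, the chance of at least one among 35 is 1 − (1 − q)^35: 16% at q = 0.5%, 30% at 1%, 51% at 2% and 83% at 5%. These values of q are assumptions. The chance of a known carrier who also scores 17% or less is no higher and cannot be derived here.

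**The case against.** The strongest reply is that the intent is plain. Footnote c, 6.3, endpoint 2 and section 1.1 all point to seeing carriers. Visit 1 is run by the PI or the Breast Care Clinic nurse practitioner, who would hardly dismiss a known carrier. The 6.3 wording is not expressly confined to tests done in the study, so it may reach an earlier result. The documents do not say whether the calculators accept a known variant; if they do, such a person might never score 17% or less. The study schema and the 6.1 workflow figure are not shown and may contain a carrier branch.

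This shows that the correction is small, not that it is unnecessary. Sensible staff would follow footnote c, but they would be departing from the text of 6.2 to do so. A branch in a figure would not remove that conflict.

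A reader might infer several stronger points that the documents do not support:

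- *Every carrier at 17% or less loses Visit 2.* No: 6.3 provides for those tested and found positive.
- *The same contradiction exists for chest radiation.* Section 1.1 does list "high-dose radiation to the chest before age 30" as a risk factor, and no later rule or data item mentions it. But no text promises a separate route, so this is an omission, not a conflict. Breast density is on the same list and is not collected either.
- *Endpoint 1 is wrong because it leaves out carriers.* The Rationale speaks of people "who have an elevated lifetime risk of BC development (>17%) or a pathogenic genetic mutation that increased the risk of BC development", but objective 1 and endpoint 1 both rest on elevated lifetime risk. A further prevalence figure would be optional reporting.
- *The labels in 6.5 single out carriers.* Both mastectomy items are labelled for 17 to 30%, which also omits those above 30%. The stated-choice item refers to top surgery for everyone. Footnote d says only that follow-up may happen. These are general weaknesses.

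**Conclusion.** The point holds in a narrow form. Sections 6.2 and footnote c give opposite instructions for a participant already known at Visit 1 to carry a variant who scores 17% or less, and no 6.3 or Appendix 2 trigger names that person. Separately, footnote d leaves out all carriers at 17% or less, although endpoint 2 counts them.

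The number affected is not given and may be zero. One such carrier could move endpoint 2 by up to 20 points, but only on the assumed denominator of 4 and within intervals that are already very wide. A reader might take this as evidence of a biased estimate; the documents do not support that. What needs correcting is a stated rule that gives the wrong advice in a case the protocol itself foresees. It is a minor correction. The conclusion rests on the printed text and on a known carrier being able to score 17% or less, which the documents neither establish nor rule out.

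**What to change.** 1. **Section 6.2.** After the 17% limit, add the condition *and no known pathogenic BC variant*. Then add the sentence: *Carriers of a pathogenic BC variant are offered Visit 2 whatever their score.*
2. **Section 6.5.** Add one intake item: *pathogenic BC variant known before enrolment (Y/N, gene)*.
3. **Footnote d and section 6.5.** Extend footnote d to *risk >17% or a pathogenic BC variant*. In 6.5, record both the mastectomy option and the stated choice on risk-reducing mastectomy for everyone in the endpoint 2 denominator: 17 to 30%, above 30%, and carriers at 17% or less.

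The cost is one intake question and minor wording in an amendment. Endpoint 1, the sample size and the analysis methods stay as they are.
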